2.8.4 Other safety data

2.8.4.1 ECG and cardiac imaging data

Baseline for ECG analysis is defined as the average of all available ECG measurements associated with the baseline assessment. Scheduled study day 1 pre-dose ECGs will be

considered to have been obtained prior to study drug administration if dosing time is missing. If a scheduled pre-dose measurement actually occurred post-dose, then the corresponding measurement will be treated and analyzed similar to an unscheduled post-dose measurement.

If a patient has more than one post-baseline measurement at a specific time point, the average of all available measurements associated with the nominal time point will be used for the analyses.

The following summary will be provided for each applicable ECG parameter:

- Frequency counts and percentages of patients having notable ECG values according to [Table 2-3](#).

Table 2-3 Criteria for notable ECG values

ECG parameter	Criteria for ECG notable values
QTcF (ms) and QD (ms)	Increase > 30 ms to ≤ 60 ms Increase > 60 ms New > 450 to ≤ 480 ms New > 480 to ≤ 500 ms New > 500 ms
QRS (ms)	Increase > 25% and QRS > 120 ms New QRS > 120 ms
HR (bpm)	Increase > 25% and HR > 100 bpm Decrease > 25% and HR < 50 bpm
PR (ms)	Increase > 25% and PR > 200 ms New PR > 200 ms

Notable ECG values (including notable QT interval values) will be flagged in the listings.

2.8.4.2 Vital signs

Vital sign parameters collected are systolic and diastolic blood pressure (mmHg), pulse rate (beats per minute), body temperature (°C), and weight (kg). Vital sign values considered notably abnormal are defined in [Table 2-4](#).

Table 2-4 Criteria for notable vital sign values

Vital sign	Criteria for clinically notable vital sign values
Systolic blood pressure [mmHg]	≥ 180 mmHg/≤ 90 mmHg with increase/decrease from baseline of ≥ 20 mmHg
Diastolic blood pressure [mmHg]	≥ 105 mmHg/≤ 50 mmHg with increase/decrease from baseline of ≥ 15 mmHg
Pulse rate [bpm]	≥ 100 bpm/≤ 50 bpm with increase/decrease from baseline of ≥ 25%
Body temperature [°C]	≥ 39.1
Weight [kg]	≥ 10% decrease/increase from baseline

Patients with any clinically notable vital sign value will be listed.

2.8.4.3 Tolerability

Tolerability of study treatments will be assessed by summarizing the number of dose interruptions and dose reductions (see [Section 2.4.1](#) for more details) by treatment group in the phase Ib part and by patient group in the phase II part. The reasons for dose interruption and dose reductions will be listed by patient and treatment group in the dose escalation part and by patient group in the dose expansion part; they will be summarized for each investigational drug by treatment group in the dose escalation part, and by patient group in dose expansion part. Cumulative dose, dose intensity and relative dose intensity will be summarized. Categories for relative dose intensity will be specified as < 0.5 , $\geq 0.5 - < 0.75$, $\geq 0.75 - < 0.9$, $\geq 0.9 - < 1.1$ and ≥ 1.1 . The number and proportion of patients within each category will be presented.

2.9 Pharmacokinetics Analyses

The pharmacokinetic parameters will be determined by profiles using noncompartmental method(s) for both MCS110 and PDR001 as presented in [Table 2-5](#), and PAS will be used in all pharmacokinetic data analysis and PK summary statistics. Patients will be removed from the estimation of certain PK parameters on an individual basis depending on the number of available blood samples. These patients will be identified at the time of the analyses.

Table 2-5 Pharmacokinetic parameters to be analyzed

AUClast	The AUC from time zero to the last measurable concentration sampling time (tlast) (mass \times time \times volume ⁻¹)
AUCinf	The AUC from time zero to infinity (mass \times time \times volume ⁻¹)
Cmax	The maximum (peak) observed plasma, blood, serum, or other body fluid drug concentration after single dose administration (mass \times volume ⁻¹)
Tmax	The time to reach maximum (peak) plasma, blood, serum, or other body fluid drug concentration after single dose administration (time)
T1/2	The terminal half-life associated with the terminal slope (λ_z) of a semi logarithmic concentration-time curve (time). Use qualifier for other half-lives
CL	The total body clearance of drug from the plasma (volume \times time ⁻¹)
Vz	The apparent volume of distribution during terminal phase (associated with λ_z) (volume)
Clast	Last observed quantifiable concentration (mass \times volume ⁻¹)
AR	Accumulation Ratio=AUClast (multiple Dose)/AUClast (single dose) (for cycle 4 only)

For phase Ib part, descriptive statistics of all pharmacokinetic parameters in the [Table 2-5](#) for both cycle 1 and cycle 4 will include arithmetic and geometric mean, median, SD, and CV, geometric CV, minimum and maximum, by treatment group. For phase II part, descriptive statistics will be conducted for the parameters, including AUClast, AUCinf, Cmax, Clast, Tmax for both cycle 1 and cycle 4 and AR only for cycle 4 by patient group.

Summary statistics will be presented for MCS110 and PDR001 serum concentrations at each scheduled time point. Descriptive graphical plots of individual and mean serum/plasma concentration versus time profiles of free MCS110, PDR001 will be generated by treatment or patient group and cycle.

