The screening period begins once the patient has signed the study informed consent. Patients will be evaluated against study inclusion and exclusion criteria ([Table 7-1](#) and [Section 5.2](#), [Section 5.3](#) and [Section 7.1.1](#)).

Treatment period

The treatment period will begin on Cycle 1 Day 1. For the purpose of scheduling and evaluations, a treatment cycle will consist of 21 days.

Further details are provided in [Table 7-1](#) and [Section 7.1.2](#).

Follow-up (FU) period

Patients will be followed up for safety evaluations 150 days after the last administration of PDR001. For patients who had to stop PDR001 treatment but continued taking MCS110 at the time of treatment stop, the follow-up evaluation will take place 90 days after the last administration of MCS110 or 150 days after the last administration of PDR001, whichever duration is longer ([Table 7-1](#) and [Section 7.1.5](#)).

Disease progression FU

Patients who discontinue study treatment for any reason other than disease progression as per irRC will be followed up for progression of disease ([Section 7.1.5](#)). The disease progression follow-up will be performed until all patients enrolled in the Phase II part of the study have had progression of disease or discontinued the study for any reason.

Survival FU

Patients enrolled in Phase Ib and Phase II part will be followed for survival ([Section 7.1.5](#)) until the end of the study is reached, unless patients withdraw consent or are lost to follow-up.

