7.2.3 Pharmacokinetics and immunogenicity assessments

PK profiles to assess PK properties of MCS110 and PDR001 will be collected from all enrolled patients. However, only the patients from Phase Ib part will have additional PK collected on day 2, 4 and 15.

Immunogenicity (IG) samples will also be collected to monitor appearance of anti-drug antibodies directed against MCS110 or PDR001. Please refer to [Table 7-6](#) and [Table 7-7](#) for details on PK and IG sample collections.

If the dosing of Cycle 4 Day 1 is delayed, the PK sampling for the full PK profile should be delayed accordingly to match the scheduled time points for Cycle 4 as outlined in [Table 7-6](#) and [Table 7-7](#). After the primary CSR data cut-off date is reached, no additional PK and IG samples will be collected for the patients still on-going on the study.

Table 7-6 Phase Ib Part: Pharmacokinetic blood collection log for MCS110, PDR001 and IG samples

Cycle	Study day	Analytes	Scheduled time point (Sampling window)	Total volume of Blood sample
1	1	MCS110, PDR001 and IG ^a	Pre-dose ^b (0 hr)	6 mL
1	1	MCS110, PDR001	1 hr (± 5 min) post end of C1D1 infusion dose ^c	4 mL
1	2	MCS110, PDR001	24 hr (± 2 hr) post dose	4 mL
1	4	MCS110, PDR001	72 hr (± 6 hr) post dose	4 mL
1	8	MCS110, PDR001	168 hr (± 8 hr) post dose	4 mL
1	15	MCS110, PDR001	336 hr (± 8 hr) post dose	4 mL
2	1	MCS110, PDR001 and IG ^a	Pre-dose ^b of cycle 2 (0 hr)	6 mL
3	1	MCS110, PDR001 and IG ^a	Pre-dosed ^b of cycle 3 (0 hr)	6 mL
4	1	MCS110, PDR001 and IG ^a	Pre-dose ^b of cycle 4 (0 hr)	6 mL
4	1	MCS110, PDR001	1 hr (± 5 min) post end of C4D1 infusion dose ^c	4 mL
4	2	MCS110, PDR001	24 hr (± 2 hr) post dose of cycle 4	4 mL
4	4	MCS110, PDR001	72 hr (± 6 hr) post dose of cycle 4	4 mL
4	8	MCS110, PDR001	168 hr (± 8 hr) post dose of cycle 4	4 mL
4	15	MCS110, PDR001	336 hr (± 8 hr) post dose of cycle 4	4 mL
5	1	MCS110, PDR001 and IG ^a	Pre-dose ^b of cycle 5 (0 hr)	6 mL
6	1	MCS110, PDR001 and IG ^a	Pre-dose ^b of cycle 6 (0 hr)	6 mL
EOT		MCS110, PDR001 and IG ^a		6 mL

Cycle	Study day	Analytes	Scheduled time point (Sampling window)	Total volume of Blood sample

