
Blood samples are to be collected from the arm opposite from infusion site, or alternatively, infusion site will need to be flushed with 10 mL of saline.
 
^a Immunogenicity (IG) (Anti-Drug [MCS110 or PDR001] Antibody): blood samples to be collected for anti-drug antibody together with PK samples
 
^b Pre-dose blood samples should be collected prior to start of infusion of any treatment
 
^c MCS110 sampling time is relative to the end of MCS110 infusion; PDR001 sampling time is relative to the end of PDR001 infusion
				

Table 7-7 Phase II Part: Pharmacokinetic blood collection log for MCS110, PDR001 and IG samples

Cycle	Study day	Analytes	Scheduled time point (Sampling window)	Total volume of Blood sample
1	1	MCS110, PDR001 and IG ^a	Pre-dose ^b (0 hr)	6 mL
1	1	MCS110, PDR001	1 hr (\pm 5 min) post end of C1D1 infusion dose ^c	4 mL
1	8	MCS110, PDR001	168 hr (\pm 8 hr) post dose	4 mL
2	1	MCS110, PDR001 and IG ^a	Pre-dose ^b of cycle 2 (0 hr)	6 mL
3	1	MCS110, PDR001 and IG ^a	Pre-dosed ^b of cycle 3 (0 hr)	6 mL
4	1	MCS110, PDR001 and IG ^a	Pre-dose ^b of cycle 4 (0 hr)	6 mL
4	1	MCS110, PDR001	1 hr (\pm 5 min) post end of C4D1 infusion dose ^c	4 mL
4	8	MCS110, PDR001	168 hr (\pm 8 hr) post dose of cycle 4	4 mL
5	1	MCS110, PDR001 and IG ^a	Pre-dose ^b of cycle 5 (0 hr)	6 mL
6	1	MCS110, PDR001 and IG ^a	Pre-dose ^b of cycle 6 (0 hr)	6 mL

Blood samples are to be collected from the arm opposite from infusion site, or alternatively, infusion site will need to be flushed with 10 mL of saline.
 
^a Immunogenicity (IG) (Anti-Drug [MCS110 or PDR001] Antibody): blood samples to be collected for anti-drug antibody together with PK samples
 
^b Pre-dose blood samples should be collected prior to start of infusion of any treatment
 
^c MCS110 sampling time is relative to the end of MCS110 infusion; PDR001 sampling time is relative to the end of PDR001 infusion
				

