10.5.4 Pharmacokinetics

The pharmacokinetic parameters will be determined by profile using noncompartmental method(s) for both MCS110 and PDR001 as presented in [Table 10-1](#), and PAS will be used in all pharmacokinetic data analysis and PK summary statistics.

Table 10-1 Pharmacokinetic Parameters to be analyzed

AUClast	The AUC from time zero to the last measurable concentration sampling time (tlast) (mass x time x volume-1)
AUCinf	The AUC from time zero to infinity (mass x time x volume-1)
Cmax	The maximum (peak) observed plasma, blood, serum, or other body fluid drug concentration after single dose administration (mass x volume-1)
Tmax	The time to reach maximum (peak) plasma, blood, serum, or other body fluid drug concentration after single dose administration (time)
T1/2	The elimination half-life associated with the terminal slope (λ_z) of a semi logarithmic concentration-time curve (time). Use qualifier for other half-lives
CL	The total body clearance of drug from the plasma (volume x time-1)
Vz	The apparent volume of distribution during terminal phase (associated with λ_z) (volume)
AR	Accumulation Ratio=Cmax (multiple Dose)/Cmax (single dose)

[figure not shown]
Descriptive statistics of all pharmacokinetic parameters will include arithmetic and geometric mean, median, SD, and CV, geometric CV, minimum and maximum. Zero concentrations will not be included in the geometric mean calculation. Since Tmax is generally evaluated by a nonparametric method, median values and ranges will be given for this parameter.

[figure not shown]
Summary statistics will be presented for MCS110 and PDR001 serum concentrations at each scheduled time point. Descriptive graphical plots of individual serum concentration versus time profiles and mean concentration versus time profiles will be generated.

Missing concentration values will be reported as is in data listings. Concentration values below Lower limit of quantitation will be handled as zero in summary statistics, and reported as is in data listings. Any missing pharmacokinetic parameter data will not be imputed.

The presence of immunogenicity for MCS110 and PDR001, at each scheduled time point, will be listed by treatment group, disease and patient. Overall immunogenicity will be summarized.

More details will be provided in SAP or separate analysis plan.

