True CBR	Probability to observe ≥ 3 responses (CR, PR or SD > 4 months) in first 20 patients	Group 2: Pancreatic cancer
		probability to observe a CBR $\geq 15\%$ with 40 patients
7.5%	18.6%	5.5%
15%	59.5%	46.1%
20%	79.4%	73.4%
30%	96.5%	96.1%

Table 3-4 Operating characteristics of the design (Group 2b)

True CBR	Groups 2b: Pancreatic cancer
	probability to observe a CBR $\geq 15\%$ with 20 patients
7.5%	18.6%
15%	59.5%
20%	79.4%
30%	96.5%

4 Change to protocol specified analyses

The following section have been updated in comparison to first SAP

Section 1.1 Study design

Section 1.2 Study objectives and endpoints

Section 2.1 Data analysis general information

Section 2.1.1 General definitions

Section 2.2 Analysis sets/Withdrawal of ICF/Subgroups

Section 2.4.1 Study treatment/compliance

Section 2.5.1 Primary endpoints

Section 2.5.2 Phase II part (Secondary endpoint)

Section 2.5.4 Supportive analyses

Section 2.7.1 Secondary endpoints

Section 2.8 Safety analyses

Section 2.8.3 Laboratory data XXXXXXXXXX

Section 3 Sample size calculation

Section 5.5 Rule of exclusion criteria of analysis sets

Section 1.1 Study design

- Updated the study design for Phase II part per protocol amendment version 5

Section 1.2 Study objectives and endpoints

- Secondary objectives, Phase II part: changed endpoint for Group 2 (Pancreatic cancer) to CBR instead of ORR

Section 2.1 Data analysis general information

- Add R version which will be used for Bayesian analyses for Phase II part.

Section 2.1.1 General definitions

- Definition of on-treatment and post-treatment assessment/event

Section 2.2 Analysis sets/Withdrawal of ICF/Subgroups

- Per-protocol Set was planned as per the protocol, but outputs were not generated because no analyses were conducted based on per-protocol set
- Add section 2.2.5 Withdrawal of Informed Consent

Section 2.4.1 Study treatment/compliance

- Definition of last date of exposure of study drug/treatment (+ 20 days instead of + 21)

Section 2.5.1 Phase II part (Primary endpoint)

- Change of group 2 (Pancreatic cancer) endpoint to CBR instead of ORR

Section 2.5.2 Phase II part (Secondary endpoint)

- Change of group 2 prior distribution
- Update design of group 2 per protocol amendment version 5

Section 2.5.4 Supportive analyses

- Change to be not applicable cause supportive analyses were not conducted.

Section 2.7.1.2 Phase II (Secondary efficacy objectives)

[figure not shown]

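### The SAP replaces the protocol's Cmax accumulation ratio with an AUClast ratio, records no reason, and sets no common interval, so the ratio can be distorted when the cycle 1 and cycle 4 profiles differ in length

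*SAP*

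**What the plan says.** Protocol Section 10.5.4, Table 10-1, gives "Accumulation Ratio=Cmax (multiple Dose)/Cmax (single dose". The same section adds "More details will be provided in SAP or separate analysis plan".

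SAP Section 2.9, Table 2-5, gives "Accumulation Ratio=AUClast (multiple Dose)/AUClast (single dose) (for cycle 4 only" and defines AUClast as "The AUC from time zero to the last measurable concentration sampling time (tlast". AR is to be summarised in both study parts. The SAP also allows patients to be dropped from individual PK parameters according to how many samples they have, with those patients identified when the analysis is done.

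SAP Section 4 is headed as changes to protocol-specified analyses but opens with "The following section have been updated in comparison to first SAP". Neither its list of sections nor its detailed items show an entry for Section 2.9 or for AR. SAP Section 1 says the plan was built on protocol version 05, whose Table 10-1 still has the Cmax ratio.

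**The concern.** There are two linked problems.

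First, a protocol-defined parameter has been changed without a record. The protocol lets the SAP add PK detail, but replacing Cmax with AUClast gives a different parameter. Section 4 does record smaller matters, such as counting exposure to 20 rather than 21 days after the last dose, so minor importance does not explain the omission.

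Second, the new parameter has no fixed interval. A ratio of AUCs measures accumulation only if both cover the same time after dose. AUClast does not ensure this, and the removal provision has no equal-interval criterion. The likely mismatch is also not random. A patient dosed in cycle 4 will normally have attended cycle 2 day 1, but one who stops before cycle 5 has no pre-dose draw to complete cycle 4. Shortening would therefore fall mostly on the numerator and go with discontinuation. At stake is the description of PDR001 and MCS110 accumulation under the secondary PK objective.

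**Working it through.** The documents state no accumulation ratio, so there is no figure to reproduce. The check compares the sampling schedules and then illustrates the effect under stated assumptions.

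**Schedule (Protocol Section 7.2.3, Tables 7-6 and 7-7).**
- Phase Ib, cycles 1 and 4: 1, 24, 72, 168 and 336 h after dose. The last draw within cycle 4 is "336 hr (± 8 hr) post dose of cycle 4", and cycle 1 has the matching draw.
- Phase II, cycles 1 and 4: 1 h and 168 h after dose.
- In both parts a pre-dose draw follows at the next cycle (C2D1 after cycle 1, C5D1 after cycle 4).
- Protocol Section 4.1 states that "a treatment cycle will consist of 21 days", so the next pre-dose draw falls nominally at 21 × 24 = 504 h.
- Protocol Section 6.1.1 allows a dose to be up to 7 days late, which moves that draw to as much as 28 × 24 = 672 h. Section 7.2.3 shifts the cycle 4 sampling when C4D1 is late but does not address a late C5D1.

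Planned lengths are therefore equal, and unequal lengths arise only from departures from the schedule.

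**Assumptions.** Linear one-compartment PK with bolus input; doses 1 to 4 given 21 days apart; the next pre-dose draw closes each profile when it exists; PDR001 half-life 20 days, range 17 to 23 (protocol, Amendment 01 rationale).

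**Formulas.** k = ln 2 / half-life. Accumulation factor at dose 4: F = 1 + e^(−21k) + e^(−42k) + e^(−63k). AUC from 0 to T is proportional to 1 − e^(−kT) after dose 1 and to F × (1 − e^(−kT)) after dose 4. With last samples at T1 and T4,

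AR = F × (1 − e^(−k·T4)) / (1 − e^(−k·T1)).

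**Numbers at half-life 20 days.** e^(−21k) = 0.483, so F = 1 + 0.483 + 0.233 + 0.113 = 1.83. The values of 1 − e^(−kT) are 0.215 at day 7, 0.384 at day 14, 0.517 at day 21 and 0.621 at day 28.

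| Cycle 1 ends | Cycle 4 ends | Situation | AR (half-life 17 to 23 days) | Error |
|---|---|---|---|---|
| same as cycle 4 | same as cycle 1 | on schedule | 1.83 (1.68 to 1.96) | none |
| day 21 | day 14 | Phase Ib, no C5D1 sample | 1.83 × 0.384/0.517 = 1.36 (1.27 to 1.44) | about −26% |
| day 21 | day 7 | Phase II, no C5D1 sample | 1.83 × 0.215/0.517 = 0.76 (0.73 to 0.80) | about −58% |
| day 21 | day 28 | C5D1 dose 7 days late | 1.83 × 0.621/0.517 = 2.20 (1.99 to 2.39) | about +20% |

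The first row holds for any common end point (day 7, 14 or 21), and the protocol's Cmax ratio takes the same value in this model. Small timing differences do not matter: 512 h in cycle 1 against 496 h in cycle 4 gives 1.79, about 2% low.

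**The case against.** The strongest reply is that the fault is conditional. Cycles 1 and 4 are sampled identically, and with equal lengths the AUClast ratio is correct. A reader might infer that an AUClast ratio is wrong in itself; the schedule does not support that.

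The SAP also has a safeguard, since patients with too few samples can be removed. That is true, but the rule refers to the number of samples, states no equal-interval requirement and is applied at analysis. Following Table 2-5 literally would keep a patient with a complete cycle 1 profile and a shortened cycle 4 profile.

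Nor do the documents say that the next pre-dose draw belongs to the preceding profile; Tables 7-6 and 7-7 list it under the following cycle. If profiles ended at the last within-cycle draw (336 h or 168 h), a missing C5D1 sample or a late C5D1 dose would do no harm. This stands as a limit on the figures, and the missing rule is itself part of what needs settling.

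The figures also cannot be carried over to MCS110, whose clearance depends on concentration (Protocol Section 1.2.2.2.1). A ratio biased upwards because cycle 1 ends at day 14 and cycle 4 at day 21 (2.46 in this model) would need a missing C2D1 sample, which early stopping does not produce in someone dosed in cycle 4.

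Finally, AR carries no hypothesis or decision rule. Cmax in both cycles and concentrations at every scheduled time are summarised too, so accumulation could still be seen elsewhere. That limits the consequence but does not make the AR row reliable.

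On disclosure, Section 4's opening line refers to changes from a first SAP that is not available here. Its heading nevertheless concerns the protocol, and it does report one departure from it (the Per-Protocol Set). A reader might infer deliberate concealment; the documents show only that no entry is visible.

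**Conclusion.** The point holds in limited form. The AR definition differs between protocol and SAP with no visible record of the change. The new definition gives the right ratio for profiles of equal length and can be materially wrong for the others. Under the stated assumptions, a PDR001 ratio of 1.83 would be reported as 1.36 in Phase Ib or 0.76 in Phase II when the C5D1 sample is missing, and as 2.20 when the C5D1 dose is 7 days late. The Phase II value would read as a fall in exposure.

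These are errors in a single patient's ratio. The documents do not show how many patients are affected, so the shift in the summary statistics cannot be stated. The primary analyses are untouched. The correction is still worth making, because the distortion is foreseeable, tied to stopping treatment, and easy to prevent.

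**What to change.** In SAP Table 2-5, define AR as AUC in cycle 4 divided by AUC in cycle 1 over the same interval after dose: 0 to 21 days, or the latest time point available in both cycles. Compute it only where both AUCs are evaluable, and state which draw closes each profile. Report the protocol's Cmax ratio alongside it. Add an entry to SAP Section 4 giving the change from Table 10-1 and the reason.

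The cost is a few lines of text. A few patients would lose their AR value or have it on a shorter interval.

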IRB/IEC/HA Approval

A copy of this amended protocol will be sent to the Institutional Review Board (IRBs)/Independent Ethics Committee (IECs) and Health Authorities.

The changes described in this amended protocol require IRB/IEC approval prior to implementation. The changes herein affect the Informed Consent. Sites are required to update and submit for approval a revised Informed Consent that takes into account the changes described in this protocol amendment.

Amendment 01 (11-Jul-2016)

Amendment rationale

The main reason for this amendment is to add more specific guidance for dose modifications and to revise definitions for dose limiting toxicities (DLTs), following Health Authority (HA) feed-back. In addition the routine chemistry lab test Lactate dehydrogenase (LDH) has been added since a recent publication suggest that TNBC and metastatic melanoma patients with aggressive tumor growth, with elevated LDH, may have less benefit of PD-1 inhibition compared to those with more slowly growing tumors (Diem et al., 2016, Nanda et al., 2016).

With the available PK data obtained from the single agent first-in-human study CPDR001X2101, an exploratory population PK (PopPK) analysis showed that the T_{1/2} of PDR001 in man is 20 [17, 23] days (mean [90% CI]). Using five times the upper limit of the half-life of 23 days and an added safety margin, the protocol is amended to increase the duration of contraception and safety follow-up periods post PDR001 treatment from 90 days to 150 days. These changes are related to an Urgent Safety Measure communicated on 08-June-2016 to all investigators.

Minor corrections of typos/clarifications of text were also made. The details are provided in the below section “Changes to the protocol”.

Study status

The CMCS110Z2102 study is currently under review by Health authorities .

Changes to the protocol

Changes to specific sections of the protocol are shown in the track changes version of the protocol using strike through red font for deletions and red underlined for insertions.

- Section 6.1.1 Dosing regimen. Adding instructions to resume treatment at a lower level after skipping an administration (if meeting criteria for DLT)
- Section 6.2.4 Definitions of dose limiting toxicities. The following Grade 4 AEs should be defined as DLTs: Electrolyte abnormalities and CK elevation

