6.1.1 Dosing regimen

Table 6-1 Dose and treatment schedule

Study treatments	Pharmaceutical form and route of administration	Dose	Frequency and/or Regimen
MCS110	Liquid concentrate in vial i.v. infusion	3 mg/kg (starting dose)	Every 3 weeks
PDR001	Powder for solution for infusion	100 mg (starting dose)	Every 3 weeks

MCS110 and PDR001 will be administered once every 3 weeks via i.v. infusions over 1 hour and 30 minutes, respectively. The drugs will be administered separately with at least a 30 min break between the two antibodies. Infusions of each antibody can be extended to up to 2 hours if clinically indicated.

Both study drugs may be infused using the same i.v. access site. The same administration sequence must be followed for all patients, i.e. PDR001 should be infused first. If an infusion reaction occurs after administration of PDR001, the subsequent MCS110 infusion must be delayed until it is safe for the patient to receive MCS110 based on the clinical discretion of the investigator. The delay between PDR001 and MCS110 infusions can be up to 4 hours if clinically indicated.

A scheduled dose of ongoing study drugs may be delayed by up to 7 days to recover from previous AEs or a missed visit (see [Section 6.3.2](#)). If a scheduled dose of ongoing study drugs is delayed longer than 7 days due to an unresolved AE, the administration should be skipped and treatment resumed at a lower dose level (if meeting criteria for DLT) at the next scheduled dose. The assessment schedule will be shifted accordingly. Dose delays refer to all ongoing study drugs: for combination treatment both MCS110 and PDR001 and for single agent treatment MCS110 or PDR001. Dose modifications should follow [Section 6.3.1](#) and [Section 6.3.2](#).

The dose for MCS110 study drug will be calculated from the individual subjects' body weight as measured at the screening visit and subsequent visits prior to the administration.

After Phase Ib part, if emerging PK, PD, and safety data indicate that a flat dosing strategy of MCS110 is appropriate, then a flat dosing strategy may be implemented in the Phase II part of the study. The PK data obtained during Phase Ib part of this study will be combined with PK data from the other MCS110 clinical studies to assess the flat dosing vs. body-weight based dosing, and a flat dose may be identified for the Phase II part of this study.

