2.1 Data analysis general information

The data will be analyzed by Novartis personnel and/or designated CRO(s) using SAS version 9.4, for Bayesian logistic regression model (BLRM) modeling, R version 3.0.2 and JAGS version 3.12 will be applied and for other bayesian analyses, R version 3.4.3 will be used. PK parameters will be calculated using non-compartmental methods available in Pharsight

Phoenix version 6.4 (or newer compatible version). Newer compatible version may be used for all programs. Any data analysis carried out independently by the investigator must be submitted to Novartis before publication or presentation.

It is planned that the data from participating centers in this protocol will be combined, so that an adequate number of patients will be available for analysis. The data will be summarized with respect to demographic and baseline characteristics, efficacy observations and measurements, safety observations and measurements, and all relevant PK and PD measurements using descriptive statistics (quantitative data) and contingency tables (qualitative data).

The study data will be analyzed and reported based on all patients' data of the Phase Ib and Phase II parts up to the time when all patients have potentially completed at least six cycles of treatment or discontinued the study. Phase Ib data and Phase II data will be reported separately. Any additional data for patients continuing to receive study treatment past the data cutoff date for the primary CSR, as allowed by the protocol, will be reported at completion of the study as defined in [\[CMCS110Z2102-CSP-Section 4.3\]](#).

The following rules will be followed for reporting results unless stated otherwise:

- Phase Ib dose escalation data: cohorts treated during the dose escalation with the same dose levels of MCS110 and PDR001 will be pooled into a single treatment group. All summaries, listings, figures and analyses will be performed by treatment group and “All Phase Ib Subjects”.
- Phase II data: All summaries, listings, figures for non-safety analysis will be reported by arm. Safety analysis of phase II will be reported by arm and “All Phase II Subjects” Column. The arms to which they were assigned at baseline based on disease types consist of the following:
 - Group 1: TNBC (naive to PD-1/PD-L1 directed therapy)
 - Group 2: Pancreatic cancer (naive to PD-1/PD-L1 directed therapy)
 - Group 3: Endometrial cancer (naive to PD-1/PD-L1 directed therapy)

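### SAP 2.9 summarises AUCinf at cycle 4 (and CL and Vz in Phase Ib) with no AUCtau and no clearance formula, so cycle 4 values include carry-over from earlier doses

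*SAP*

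**What the plan says.** SAP 2.9 treats the two parts differently.

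- **Phase Ib:** "descriptive statistics of all pharmacokinetic parameters in the [Table 2-5](#) for both cycle 1 and cycle 4". Table 2-5 contains AUCinf, CL and Vz, so all three are summarised at cycle 4.
- **Phase II:** a shorter list, "including AUClast, AUCinf, Cmax, Clast, Tmax for both cycle 1 and cycle 4", plus AR at cycle 4 only. AUCinf is kept at cycle 4. CL and Vz are not listed.

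Table 2-5 defines AUCinf as "The AUC from time zero to infinity" and CL as "The total body clearance of drug from the plasma". It gives no formula for CL or Vz and has no AUCtau. On method, SAP 2.1 says "PK parameters will be calculated using non-compartmental methods available in Pharsight" Phoenix, which names the software but not the formula. Nothing in SAP 2.9, SAP 2.9.1 or Protocol 10.5.4 restricts AUCinf, CL or Vz to the first dose, or corrects for drug already present before the dose.

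Protocol 6.1.1 fixes the interval: "MCS110 and PDR001 will be administered once every 3 weeks via i.v. infusions". Protocol Tables 7-6 and 7-7 place a PK profile after the cycle 4 day 1 dose, and a pre-dose sample at cycle 5.

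**The concern.** After a first dose, the area from time zero to infinity is the total exposure produced by that dose, and Dose/AUCinf is clearance. After a fourth dose it is not. Drug from doses one to three is still circulating, and its remaining area is added to that of the new dose. The cycle 4 value is then neither the exposure from one dose nor the exposure over one dosing interval.

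Set beside cycle 1, AUCinf would rise through carry-over alone. If CL and Vz are derived from it, both would appear to fall. A reader could take this for clearance that changes with time. Protocol 1.2.2.2.1 reports that MCS110 clearance does fall as dose rises, so an artefact in that direction would not look implausible. Characterising the PK of the two drugs in combination is a listed secondary objective.

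**Working it through.** **Inputs**

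- Dosing interval: 21 days (Protocol 6.1.1), so cycle 4 day 1 is the fourth dose.
- PDR001 half-life: the Amendment 01 rationale states that the half-life "of PDR001 in man is 20 [17, 23] days (mean [90% CI"). This comes from an exploratory population PK analysis.
- MCS110: concentration-dependent clearance with target-mediated disposition, and no numerical half-life (Protocol 1.2.2.2.1).
- Assumptions: linear one-compartment kinetics, with four equal doses given on schedule.

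**Check of the model.** The documents state no accumulation or bias figure to reproduce. Protocol Table 14-11 does convert PDR001 doses to Q3W equivalents by matching AUC over 6 weeks. In the same model, the relative AUC over 42 days is the sum over doses of 1 − 2^(−(42−t)/20):

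- Q3W (days 0, 21): 0.767 + 0.517 = 1.284
- Q2W (days 0, 14, 28): 0.767 + 0.621 + 0.384 = 1.772, ratio to Q3W 1.380
- Q4W (days 0, 28): 0.767 + 0.384 = 1.151, ratio to Q3W 0.897

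| Flat dose (mg) | Model Q3W equivalent (mg) | Table 14-11 (mg) |
|---|---|---|
| 80 Q2W | 110.4 | 110 |
| 240 Q2W | 331.3 | 330 |
| 800 Q2W | 1104.4 | 1110 |
| 240 Q4W | 215.2 | 220 |
| 400 Q4W | 358.7 | 360 |

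All agree within 3%. The agreement is about as good at 17 and 23 days, so it supports the model's form rather than the particular half-life.

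**Carry-over in AUCinf.** Let r = 2^(−21/t½) be the fraction remaining after one interval. By superposition, AUCinf measured from the fourth dose, divided by single-dose AUCinf, is

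1 + r + r² + r³ = (1 − r⁴)/(1 − r).

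At 20 days, r = 0.483 and the ratio is 1 + 0.483 + 0.233 + 0.113 = 1.829.

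**CL and Vz, if CL = Dose/AUCinf.** The shortfall is 1 − 1/ratio = 1 − 1/1.829 = 45.3%. Vz = CL/λz has the same shortfall.

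**CL, if Dose/AUCtau is used instead.** At the fourth dose, AUCtau is (1 − r⁴) times single-dose AUCinf, which is 0.946. Dose/AUCtau is therefore 1/0.946 = 1.058 times true CL, or 5.8% too high, because steady state is not quite reached.

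**Extrapolated share of cycle 1 AUCinf**, with the last sample at day 21: this equals r.

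| PDR001 half-life (days) | r, also the cycle 1 extrapolated share | Cycle 4 / single-dose AUCinf | Cycle 4 CL and Vz error if Dose/AUCinf | Cycle 4 CL error if Dose/AUCtau |
|---|---|---|---|---|
| 17 | 0.425 | 1.68 | −40.5% | +3.4% |
| 20 | 0.483 | 1.83 | −45.3% | +5.8% |
| 23 | 0.531 | 1.96 | −49.1% | +8.6% |

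The range reflects uncertainty in the mean half-life, not variation between patients. For MCS110, superposition does not hold and there is no half-life to enter, so no figure is given.

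**The case against.** The strongest reply is that the SAP never says CL is Dose/AUCinf. It defines CL in words and names non-compartmental software. If the analyst uses Dose/AUCtau at cycle 4, the PDR001 error is about +6%, not −45%. That stands, and it makes the 45% conditional. It does not rescue AUCinf, which is requested by name at cycle 4 in both parts and contains carry-over whatever formula is used for CL.

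Second, part of what is needed is already planned. AUClast and Clast are reported at both cycles, and concentrations are summarised at each scheduled time point. Cycle 4 AUClast approaches an interval AUC if the cycle 5 pre-dose sample closes the profile. An accumulation ratio at cycle 4 warns readers to expect carry-over, and Phase Ib also reports half-life at both cycles, which carry-over would not change under the linear model. This limits the harm. It leaves the AUCinf request uncorrected, and the SAP does not say that the cycle 5 sample closes the cycle 4 profile.

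Third, SAP 2.9 allows patients to be removed from certain parameters according to the number of samples available. That is a rule about sample counts decided at analysis, not a limit on the extrapolated share.

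A reader might also infer that a fall in CL would be mistaken for a drug-drug interaction. The documents give little support for this: cycles 1 and 4 are both combination treatment and no single-agent PK arm is planned. Apparent time-dependence is the more realistic misreading.

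**Conclusion.** Wrong as written, but minor. SAP 2.9 requests a cycle 4 AUCinf that does not measure exposure from one dose. In Phase Ib it also requests cycle 4 CL and Vz without saying how they are computed. For PDR001 the cycle 4 AUCinf is 1.83 times (1.68 to 1.96) the single-dose value. CL and Vz would be about 45% (41% to 49%) too low only if they are derived from it. Both figures rest on linear one-compartment kinetics, a 20-day (17 to 23) half-life and four equal doses on schedule.

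Three wider readings are not supported. The SAP does not prescribe a biased clearance formula; it omits the formula. The 45% does not extend to MCS110. The CL and Vz problem does not arise in Phase II, where those parameters are not listed. Cycle 1 values are free of carry-over, although about 48% of PDR001 AUCinf would be extrapolated there even with a 21-day sample. The analyses are descriptive and secondary, and no primary endpoint depends on them.

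**What to change.** In SAP 2.9 and Table 2-5:

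1. Add AUCtau, from 0 to 21 days, closed at cycle 4 by the cycle 5 pre-dose sample. State how profiles without that sample are handled.
2. At cycle 4, report AUCtau, Cmax, Ctrough and CL as Dose/AUCtau. Drop AUCinf in both parts, and any CL or Vz based on it.
3. Note that the fourth dose is slightly short of steady state, so PDR001 Dose/AUCtau is expected to be about 6% (3% to 9%) too high.
4. Write out the formulas for CL and Vz, and restrict AUCinf and the CL and Vz derived from it to cycle 1.
5. State a limit on the extrapolated share of cycle 1 AUCinf, and flag or exclude values above it.

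The cost is a few lines, by amendment or addendum as SAP section 1 provides, with no new samples. The real downside is that fewer cycle 1 AUCinf, CL and Vz values would be reported. With about 48% extrapolation expected for PDR001, a strict limit could remove many of them, and flagging may then serve better than exclusion. At cycle 4, patients without a cycle 5 pre-dose sample would not have a fully observed AUCtau.
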